ii) Clinical Significance	page 27
III) Research Design and Methods	page 29
IV) Protection of Human Subjects	page 33
V) Adequacy of Protection against Risks	page 35
VI) Subject Safety and Minimizing Risks	page 42
VII) Consultants	page 43
VIII) Facilities Available	page 44
IX) Appendices	page 45
X) References	page 71

I) SPECIFIC AIMS

i) Aim 1

The primary outcome is to assess the safety and toxicity profile of the combination of famotidine and oral n-acetyl cysteine in adult outpatients with newly diagnosed SARS-CoV-2 infection.

ii) Hypothesis 1

We hypothesize that the combination of famotidine and n-acetyl cysteine are a safe combination of therapies in adult outpatients with newly diagnosed SARS-CoV-2 infection.

iii) Aim 2

The secondary outcome is to assess whether certain markers (e.g., IL-1 β , IL-2, IL-6, Tryptase, Glutathione, F2-Isoprostane/Creatinine, N-methylhistamine, CAP-SYM 18, IPSS and CURB-65) are predictive of outcomes and/or treatment response.

iv) Hypothesis 2

We hypothesize that treatment with the combination of n-acetyl cysteine and famotidine in addition to the potential for reducing the primary endpoint of risk of hospitalization may also affect specific markers of infection which may prove useful surrogates for predicting the severity of the infection.

II) BACKGROUND AND SIGNIFICANCE

i) Background

N-Acetyl Cysteine (NAC) is a prodrug to L-cysteine which is a precursor to the biologic antioxidant glutathione. Administration is FDA approved for acetaminophen poisoning for which it is nearly 100% effective if given within 8 hours¹ and works through replenishing glutathione stores.²

Famotidine is a histamine-2 (H₂) receptor antagonist. Administration is approved in adult and pediatric patients 40 kg and above for the treatment of active duodenal ulcer, active gastric ulcer, symptomatic non-erosive gastroesophageal reflux disease (GERD), and erosive esophagitis due to GERD if diagnosed by biopsy. Administration is also approved in adults for the treatment of pathological hypersecretory conditions (e.g., Zollinger-Ellison Syndrome, multiple endocrine neoplasias) and for the reduction of the risk of duodenal ulcer recurrence.

There have been no studies on the use of the combination of FAM and NAC in the treatment of outpatients who test positive for SARS-CoV-2 infection.

a) Biochemical rationale

1. **Angiotensin Converting Enzyme 2 (ACE2) is SARS-CoV-2 Virus Binding Site**

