In addition to the mechanisms of actions previously described, the effect NAC exerts on autophagy could prove synergistic in the potential to reduce the severity of a SARS-CoV-2 infection. There is a body of literature since 2004 in coronaviruses to include mice (MHV),¹⁶⁵ pig (PEDV and TGEV)^{166,167} and most notably the human coronavirus, SARS-CoV,¹⁶⁸ that demonstrates that coronaviruses create Double-Membrane Vesicles (DMV) from endoplasmic reticulum under oxidative stress. It seems that the coronavirus components are shuttled around in these DMVs. It has been demonstrated that depletion

of LC3-I can be rate limiting in viral replication.¹⁶⁹ It seems LC3-II normally decorates autophagosomes and LC3-I normally decorates lysosomes. It turns out that the coronaviruses DMVs are also decorated with LC3-I. In a 2018 in-vitro study of cardiomyocytes and in-vivo in rats, NAC increased the ratio of LC3II/I and reduced LC3-II autophagic flux.⁵⁹ These findings suggest that NAC triggers the accumulation of autophagosomes, which is the result either of increased synthesis or decreased degradation and that the availability of LC3-I for the formation of DMVs may be significantly decreased by NAC. **Therefore, by reducing ROS, inhibiting autophagy, inhibiting apoptosis, and potentially limiting LC3-I, these effects would potentially result in synergy between FAM and NAC to reduce the severity of a SARS-CoV-2 infection.**

Finally, because the dose limiting toxicity of NAC appears to be an anaphylactoid reaction, the combination has the potential to be synergistic if for no other reason than to allow higher doses of NAC to be tolerated orally through the action of FAM as an antagonist of the histamine-2 receptor.

ii) Clinical Significance

Rationale for a clinical trial

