Given the existing biochemical data to suggest FAM inhibits suppression of intraepithelial lymphocytes by histamine and Mast Cell release of histamine; the correlation of severity of tissue fibrosis and thrombosis with ACE2 depletion; the ability of NAC to reduce oxidative stress, which appears related to severity of the SARS-CoV-2 infection; the ability of NAC to prevent tissue fibrosis, thrombosis and reduce viral replication; the favorable side effect profiles of FAM and NAC; the wide prevalence of SARS-CoV-2 infection and its substantial mortality rate; and, the lack of vaccine or proven therapies for non-hospitalized patients who have tested positive for a SARS-CoV-2 infection; a clinical trial of the safety and efficacy of the combination of NAC and FAM is justified. These medications are readily available and their combination does have the possibility of reducing the severity of infection and mortality for these patients (see figure 9).¹⁷⁰

[figure not shown]

Figure 9: A cartoon drawing¹⁷⁰ of the putative effect of FAM to reduce inhibition of Intra-Epithelial Lymphocytes and of NAC to reduce severity of infection through reduction of oxidative stress and reduction of viral replication

III) RESEARCH DESIGN AND METHODS (including data analysis)

i) Study Design - Parallel Phase I/II Clinical Trial

The proposed parallel phase I/II design allows for simultaneously evaluating the safety and efficacy of combination dose levels and to select the optimal combination dose. The trial is started with an initial period of dose escalation, and then patients are randomly assigned to permissible dose levels. Bayesian posterior probabilities are used in the randomization to adaptively assign more patients to doses with higher efficacy levels. Combination doses with lower efficacy are temporarily closed and those with intolerable toxicity are eliminated. The trial is stopped if the posterior probability for safety, efficacy or futility crosses our pre-specified boundaries. This design has been shown in simulations to save sample size, to have better power and efficiently assigns more patients to doses with higher efficacy levels.¹⁷¹

Phase I Portion (Dose Escalation Phase)

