The doses to be tested for famotidine are 20 mg thrice daily, 40 mg thrice daily, 80 mg thrice daily and no famotidine. The doses to be tested for n-acetyl cysteine are 600 mg thrice daily, 1200 mg thrice daily and 1800 mg thrice daily. The dose combinations are labelled 1 through 12 and are zoned as illustrated in Figure 10. The first zone has the combination of the lowest dose of each drug. The second zone has the combination of the lowest dose of each drug with the middle dose of each drug. The dose escalation starts with the first zone and follows with the second zone and then each combination of doses in the zone next closest to the coordinate

[figure not shown]

Figure 10. Dose Combinations of N-Acetyl Cysteine and Famotidine

origin shown in figure 10. Combination doses in the same zone are tested simultaneously using block randomization to control the number of patients for each open dose. Some combinations doses may close, in which case blocked randomization is applied to the remaining open combination doses in the same zone. A modified “3+3” design¹⁷² will be used for the initial dose escalation.

To find acceptable dose levels any grade 3 or higher toxicity will be considered a dose-limiting toxicity (DLT). The modified “3+3” design proceeds as described below. Three patients receive dose level 1. Their responses determine the subsequent steps as described in the following decision rules.

- (1) If two patients (2/3) experience DLT, then we close dose level 1 and all larger doses to testing.
- (2) If no patient experiences DLT, then we designate dose level 1 as an admissible dose, and open doses in zone 2 for testing.
- (3) If only one of the first three patients (1/3) experiences DLT, then we assign three more patients to dose level 1. In this case, we assign up to six patients to this dose, and the following decision rules apply:
 - a. If only one of the six patients (1/6) experiences DLT, then we designate dose level 1 as an admissible dose, and open doses in zone 2 for testing.
 - b. If two of the six patients (2/6) experience DLT, then we designate dose level 1 as an admissible dose, and doses in zone 2 and higher are closed to testing.
 - c. If more than two of the six patients (>2/6) experience DLT, then we close dose level 1 to testing, and we also close doses in zone 2 and higher.

ii) Study Procedure

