DLT based on the trial rules and assuming the IRB and DSMB which will have also been notified of the DLT, have not imposed further restrictions, the PI will obtain from the Statistical Lead Investigator a new “Dynamic Randomization Lookup Table.” The old “Dynamic Randomization Lookup Table” will be removed from the REDCap® “File Repository” but an electronic copy will otherwise be maintained by the Lead Statistical Investigator. The new “Dynamic Randomization Lookup Table” will be uploaded into the file repository and the User Rights to the enrollment and randomization data entry forms in REDCap® will be restored.

After the investigator has determined the trial arm to which the subject has been randomized through the two-step process as described above, the investigator will verify that they correctly accessed the “Dynamic Randomization Lookup Table” in the form entitled, “COVID-19 Test Result and Drug Randomization Case Report Form.” The remainder of the form will be completed to include entry of the trial arm and verification that the correct prescription has been entered. The subject will be notified of the randomization and prescription entry. Whenever, a Randomization CRF is saved, the PI will receive an immediate electronic notification via REDCap® and the PI will then complete the Investigator Assignment Form in REDCap®, a copy of which can be found in the Appendix. It is through this form that the subject will be assigned to an individual Investigator and an individual Research Assistant for the remainder of their trial participation. The assigned Investigator and Research Assistant will be immediately notified electronically via REDCap®. The subject will be notified by the PI to which Investigator and Research Assistant they have been assigned. Unless the subject has declined a Vivify® electronic device, such device, the trial medication and paper copies of the medication log and daily diaries will be delivered to the subject’s home within 24 hours of randomization by a courier who will have the appropriate training and PPE. If the subject has declined a Vivify® electronic device, they will be required to pick-up their study drugs and paper copies of their forms at an Upstate Pharmacy.

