After a subject has been randomized to a combination of trial drugs the Prisma-Health lab will be notified to process the first tube of blood for a determination of the subject’s blood type and Rh factor. The second tube will be sent to Kiyatec® to determine their Glutathione level, a cytokine panel (IL-1 β , IL-2, IL-6, IL-8, IL-10, IFN γ , TNF α and GM-CSF), and their tryptase level. The collected urine sample will also then be sent to Kiyatec® to measure the subject’s F2-Isoprostane level, creatinine level, a cytokine panel (IL-1 β , IL-2, IL-6, IL-8, IL-10, IFN γ , TNF α and GM-CSF), n-methylhistamine level and TMRSS2 levels. The research labs will be held, and the tests will only be performed if the subject is randomized to take an investigational

drug. Otherwise the specimens will be discarded. The lab evaluations to be performed by Kiyatec® will be kept frozen and typically run in batches of 40.

If the SARS-CoV-2 test results are negative after enrollment, the subject's participation in the trial will be completed and randomization to an investigational drug will not occur. An alert will be triggered within REDCap® with an immediate electronic notification to the PI both when a subject has been enrolled and when they have been randomized. When a zone has completed accrual, a text message will be sent by the PI to all investigators that the trial is temporarily closed to accrual, and the enrollment and randomization forms in REDCap® will be taken offline. When all subjects within the current zone have completed the trial, and the trial is not closed due to toxicity, the next zone will be opened. All Investigators will be notified by text message from the PI when a new zone is open and the enrollment and randomization forms in REDCap® will be placed back online.

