Subjects will be contacted weekly at minimum by the assigned Research Assistant and the assigned Investigator. It will be the responsibility of the assigned Investigator to ensure this happens correctly. Depending how a subject is doing clinically, an Investigator will have the discretion to perform more frequent contacts. These contacts will preferably be done with both a video and audio connection for which the Vivify® devices are capable. A telephonic contact will be discouraged but will be permissible for those who do not have a Vivify® device or for whom an acceptable audio-video connection cannot otherwise be established. Data will be collected and recorded for these contacts on the appropriate REDCap® form, i.e., Research Assistant Weekly Assessment, or Investigator Weekly Assessment. It will be the responsibility of the assigned Research Assistant to enter weekly data from the patient's medication log and daily diaries into the REDCap® forms, Daily Medication Log and Daily Diary. If any new medications are started or any non-trial medications are changed by either the Investigator or any other provider involved in the subject's care as documented in EPIC, the Research Investigator will document such changes using the REDCap® form, New Medications. At the end of every evaluation by the assigned Investigator, the Investigator will document in the REDCap® form their assessment which must be one of the following: 1, Continue on Study Without Change; 2, Have made arrangements for short interval follow-up with myself; 3, Discontinue Study; 4, Recommend Evaluation in ER; 5, Recommend Evaluation by Primary Provider; 6, Recommend Dose Reduction in one or both Trial Medications. If the Investigator Documents any assessment other than "Continue on Study Without Change", an electronic notification will immediately be sent to the PI notifying the PI of the Investigator's Assessment. If the Investigator's assessment is to recommend a dose reduction, they will be directed to document such on the REDCap® form, Trial Drug Adjustment. Within this form, the new dosages will be documented, to include the possibility of discontinuing either or both medications. Additionally, the Investigator will be required to identify whether the adjustment is being made due to a drug toxicity. If the Investigator documents that the adjustment is made due to a drug toxicity upon saving the form an immediate electronic notification will be made to the PI and Chair of the DSMB. The PI will then complete the REDCap form "NCI Adverse Event Serious Adverse Event CTCAE v5." This is an extensive form for which the PI will complete for any AE or SAE. It is comprehensive as it includes the entirety of the CTCAE v5 to include every possible grade of toxicity. Through branching logic, it minimizes the task of data entry only to the particular organ systems or laboratory values involved, an allows the PI to easily document all the data necessary for AE and SAE determination so that the IRB, DSMB and FDA can all be notified as necessary and within the required timelines as described more fully in the "Protection Against Risk" section below.

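### Does the dose-limiting toxicity rule need to state whether COVID-19 events count, and which causality categories and severity scale apply?

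*Combined protocol and SAP*

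**What the plan says.** Section III.i, Phase I Portion, holds the only definition of a dose-limiting toxicity (DLT): "any grade 3 or higher toxicity will be considered a dose-limiting toxicity (DLT". A modified 3+3 rule acts on the count. No DLT in three patients, or one in six, opens zone 2. Two in six keeps dose level 1, but "doses in zone 2 and higher are closed to testing". Two in three, or more than two in six, closes dose level 1 and everything above it.

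Other places bear on what toxicity means:

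- Aim 1 (I.i) is to "assess the safety and toxicity profile of the combination of famotidine and oral n-acetyl cysteine".
- The background (II.i) says that "the dose limiting toxicity of NAC appears to be an anaphylactoid reaction".
- The design overview (III.i) separates two reasons for acting on a dose: "Combination doses with lower efficacy are temporarily closed and those with intolerable toxicity are eliminated".
- The study procedure (III.ii) lets a new zone open when "the trial is not closed due to toxicity, the next zone will be opened".
- The outpatient follow-up text (III.iv.e) asks the investigator whether a dose adjustment was due to a drug toxicity. Of the CTCAE v5 form it says: "This is an extensive form for which the PI will complete for any AE or SAE".
- Total Planned Enrollment (IV.ii) assumes a drug limiting toxicity rate of 5% to 8% in the simulation. It gives hospitalization rates of 20% to 5% for the adaptive phase, in a sentence that breaks off.
- Protection against Risk (V.ii) defines an adverse event without regard to cause and mentions the infection as a possible cause. It lists five causality categories and has a severity table without grade numbers, whose Severe row includes hospitalization.

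**The concern.** The rule does not say which causality categories count, what happens to a grade 3 event explained by COVID-19, or which scale supplies the grade. The population is newly infected outpatients, some of whom will be admitted because of the disease. If the word any is read literally, the cause-neutral adverse event definition is carried into the rule, and the Severe row is taken as grade 3, then a COVID-19 admission is a DLT.

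Two things would then be at stake. Disease progression could close higher combinations without any drug toxicity. And the 5% to 8% fed into the simulation would not be the rate of the event being counted, so the expected number of subjects would refer to something else.

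**Working it through.** **The plan's own figure.** IV.ii reports an 83% chance that 27 to 33 subjects are needed. This does not reproduce with the 12 combinations in III.i. Twelve doses at three patients each need 12 × 3 = 36 if nothing closes, so for any zone layout the chance of 27 to 33 is at most 1 − P(a dose clears)^12. With the clearing probabilities derived below, that is about 28% at a DLT rate of 5% and 54% at 8%. A nine-combination grid with expansions only comes close: 81.3% at 6.5% (88.9% at 5%, 73.0% at 8%). The mismatch comes from the number of combinations, not from what counts as a DLT, so it does not bear on this point.

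**Dose level 1 under the written rule.** Let p be the chance that one patient has a DLT. Zone 2 opens after 0/3, or after 1/3 followed by 0/3:

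P(opens) = (1−p)³ + 3p(1−p)² × (1−p)³

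The rule does not mention 3/3; it is treated like 2/3.

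- p = 0.05: 0.8574 + 0.1161 = 0.9734, so escalation is blocked with probability 2.7%.
- p = 0.08: 0.7787 + 0.1582 = 0.9369, blocked 6.3%.

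**What if COVID-19 admissions counted.** With admission rate h independent of drug DLTs, and every admission grade 3 or higher, p = 1 − (1 − drug rate)(1 − h).

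| h | p (drug 5%) | blocked | p (drug 8%) | blocked |
|---|---|---|---|---|
| 0 | 0.050 | 2.7% | 0.080 | 6.3% |
| 5% | 0.0975 | 9.0% | 0.126 | 14.0% |
| 10% | 0.145 | 17.6% | 0.172 | 23.2% |
| 15% | 0.1925 | 27.5% | 0.218 | 33.1% |
| 20% | 0.240 | 37.8% | 0.264 | 43.0% |

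Weaker versions at a 5% drug rate:

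- Half of admissions counted: p = 1 − 0.95 × 0.975 = 0.07375, blocked 5.4% at h = 5%; p = 1 − 0.95 × 0.90 = 0.145, blocked 17.6% at h = 20%.
- Full overlap of admissions with drug DLTs: p = 0.05, blocked 2.7% (no change) at h = 5%; p = 0.20, blocked 29.1% at h = 20%.

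**Which reading the text supports.**

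1. *Term.* III.i counts toxicity. The cause-neutral sentence in V.ii defines an adverse event. III.iv.e keeps the two apart: drug toxicity for a dose adjustment, any adverse event for the CTCAE form.
2. *Rates.* IV.ii states 5% to 8% for drug limiting toxicity and 20% to 5% for hospitalization, as separate quantities for separate phases. If all admissions counted and ran near 20%, a total DLT rate of 5% to 8% would be impossible. Stating both suggests that the first excludes the second.
3. *Role of hospitalization.* Hypothesis 2 (I.iv) treats hospitalization risk as something treatment may reduce. The design overview acts on efficacy and on toxicity separately. Counting admissions as DLTs would merge the two.
4. *Scale.* The V.ii severity table starts at None and carries no numbers. The CTCAE v5 form is described in III.iv.e as covering every grade of toxicity, so it is the only source of a grade 3.

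**The case for a change.** The best case for acting is that none of these pointers is a rule. Even if only drug-related events count, the plan does not say whether a possibly related event does. V.ii assigns that category when two of four criteria are met, and the listed famotidine reactions include fever, difficulty breathing and pneumonia, all of which overlap with COVID-19. Arm assignment is known to investigators, so a contested event would be attributed with knowledge of the dose. The procedure for changing the randomization table acts on a "DLT based on the trial rules and assuming the IRB and DSMB which will have also been notified of the DLT", which leads back to the same undefined count.

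Part of this stands. A written threshold is absent, and borderline attribution needs judgement. But attribution is not left to one investigator: V.ii has causality determinations reviewed by the sponsor-investigator and the Data and Safety Monitoring Board, and gives the board, in consultation with the IRB, the decision on closing an arm. III.ii suspends enrollment and randomization while a DLT-driven table change is made, with both bodies notified. A COVID-19 admission would therefore not be counted unnoticed. Stating a threshold would not remove the judgement about whether a given event meets it.

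**Conclusion.** No change is needed. The definition lacks detail, but the people who apply it have the information and the authority to fill the gap, and the surrounding text points them to drug-attributed events graded by CTCAE v5. On that reading the 5% to 8% simulation input is unaffected, and dose level 1 blocks higher doses with probability 2.7% to 6.3%.

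The larger figures are a what-if. Reaching 37.8% (43.0% at the 8% drug rate) requires that all admissions count, that all are grade 3 or higher, that they are independent of drug DLTs, and that 20% hospitalization applies during escalation. That last figure is the top of a range given for the adaptive phase in a sentence whose end cannot be seen. Under the mildest assumptions (5% drug rate, 5% hospitalization, full overlap) the effect is nil. The range does not show that the rule as written gives a wrong result.

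Re-running the simulation would matter only if the sponsor adopted an all-cause definition. An all-cause table of severe events and admissions by arm could be drawn from forms already collected, so it is a reporting preference. These conclusions cover dose level 1 only. No whole-trial effect is claimed, because the zone figure is not shown and the 5% to 8% range is not mapped to doses.

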The randomization process will be performed using the Randomization module within REDCAP®. This will be performed through use of the data entry form entitled, “COVID-19 Test Result and Drug Randomization Case Report Form.” If the subject has a Rapid Test Performed in the ED and a positive result is obtained prior to discharge, the Co-Investigator who enrolled the subject will be able to access this form and perform the randomization. Otherwise, the randomization will be performed by the PI. Due to the trial design as a Phase I trial, the number of subjects on any arm can vary from zero to six depending on any dose limiting toxicities that may occur. Also, a new zone in the trial will not be able to open until all subjects in the previous zone have completed the trial. Therefore, the randomization process will be dynamic which REDCap® is incapable of handling directly but is capable of handling indirectly in a two-step process as described below. Prior to the start up the trial, a randomization lookup table will be uploaded into REDCap®, which will be nothing more than an ordered table from one to one hundred. While this may seem trivial, it is utterly essential in order to harness the power of REDCap® for a dynamic randomization process. After an investigator has performed the randomization task in REDCap®, the randomization number will be returned from this table. The investigator will then be required to lookup manually the arm to which the subject has been randomized in a file called “Dynamic Randomization Lookup Table” which they will only find within the “File Repository” in REDCap®. An example of this file can be found in the Appendix below. This file will be created prior to the trial initiation by the Lead Statistical Investigator initially assuming three subjects for each trial arm. Anytime, a change is needed to the “Dynamic Randomization Lookup Table” due to a DLT, the PI will suspend the ability for anyone to enroll or randomize a subject through the “User Rights” feature of REDCap® which can be used to restrict access by role to data entry forms. Once a decision has been made about either expanding or closing a trial arm due to a

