Other adverse reactions that were reported in less than 1 % of subjects in clinical trials include: fever, abnormal weakness or lack of energy; fatigue; heart palpitations; elevated liver enzymes; vomiting; nausea; abdominal discomfort; decreased appetite; dry mouth; decreased platelet counts in your blood; swelling of the tissue around your eyes; rash; eye redness and irritation; difficulty breathing; muscle pain; joint pain; seizure; hallucinations; depression; anxiety; decreased interest in sexual intercourse; difficulty falling asleep; prolonged sleeping; dry skin; flushing; ringing in your ears; altered sense of taste; and difficulty in men with achieving erections capable of intercourse. The following have also been reported during post-approval use of famotidine: changes to your heart by effecting the rhythm in which it beats; jaundice; inflammation and possible damage to your liver; decreased levels of white blood cells, red blood cells or platelets which could be life threatening; allergic reaction which could be life-threatening; rapid swelling of soft tissues often involving tissue around the face, limbs or genitals; hives; muscle damage; muscle cramps; confusion; agitation; tingling, numbness, or burning sensation in the skin often involving hands, feet, arms, or legs; pneumonia; and rash and blistering which could be life threatening.

The main risks to N-Acetyl Cysteine include but are not limited to the following: allergic reaction which could be life threatening; rash; itching; nausea or vomiting.

ii) Total Planned Enrollment

Estimated Number of Subjects: 42

We estimate a sample size of around 42 subjects for a 3+3 dose escalation period of our parallel phase I/II trial design. Based on our simulation of the phase I period of the trial and an assumption that a drug limiting toxicity ranges between 5% and 8%, we found an 83% chance that between 27 and 33 subjects would be required. During the adaptive phase of our trial with predicted rates of hospitalization ranging from 20 to 5% as shown in

iii) Does this study involve any of the following: prisoners, pregnant women, children, institutionalized individuals, or other populations that may be considered vulnerable?

No

iv) Does this study seek to exclude a specific racial, ethnic, or gender group? Include a compelling rationale if so.

No

v) Sources of Materials

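### Cheap improvement to consider: after a related life-threatening or fatal event, the enrollment hold can be lifted on DSMB non-objection while the board's review is still open

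*Combined protocol and SAP*

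**What the plan says.** **Dose rules** (III, i, Phase I Portion). The DLT definition is that "any grade 3 or higher toxicity will be considered a dose-limiting toxicity (DLT"). Rule (3) then reads: "If only one of the first three patients (1/3) experiences DLT, then we assign three more patients to dose level 1". The rules are written for dose level 1. I take them to apply to every combination, because the Study Procedure section allows up to six subjects on any arm depending on DLTs. Neither the definition nor the rule separates grade 3 from grades 4 and 5.

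**Hold and release** (III, ii, Study Procedure). When a DLT means that the randomization lookup table must change, "the PI will suspend the ability for anyone to enroll or randomize a subject". Release begins "Once a decision has been made about either expanding or closing a trial arm due to a" DLT. That decision is to follow the trial rules, and it is qualified by "assuming the IRB and DSMB which will have also been notified of the DLT, have not imposed further restrictions". The new table "will be uploaded into the file repository and the User Rights to the enrollment and randomization data entry forms" are restored.

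**Oversight** (V, ii, Protection against Risk). Life-threatening or fatal events are reported immediately to the medical monitor, who chairs the DSMB, and to the IRB. The DSMB reviews causality determinations. In consultation with the IRB it determines whether the trial or an arm closes, temporarily or permanently, and whether subjects must be notified.

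**Foreseen risk.** The Background (II, i, b, item 14) says that "the dose limiting toxicity of NAC appears to be an anaphylactoid reaction". Risks To The Subjects (IV, i) lists for NAC "allergic reaction which could be life threatening; rash; itching; nausea or vomiting", and lists life-threatening allergic reaction among the post-approval reports for famotidine.

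**The concern.** Safety is the primary outcome. The plan gives the DSMB the two judgements that matter after a serious related event: whether the drugs caused it, and whether the arm should stay open. The release step does not wait for either. It requires that the board has been told and has not restricted the trial, which is different from the board having cleared the event.

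The step that resumes dosing is also driven by DLT counts that ignore grade. One anaphylactic death among three subjects and one grade 3 laboratory toxicity among three subjects lead to the same instruction. At stake is whether three further subjects receive a dose while the review of a related death or life-threatening reaction at that dose is unfinished.

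**Working it through.** The plan gives no figure on this point, so there is none to reproduce. The check is a trace through the text, followed by some arithmetic for context.

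**1. The path after one related grade 4 or 5 event among three subjects.** I take grades 4 and 5 to be the life-threatening and fatal rows of the plan's severity table.

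- *Classification:* the event is a DLT, and 1/3 triggers rule (3).
- *Hold:* the lookup table must change, so the PI suspends enrollment and randomization.
- *Notification:* the DSMB chair and the IRB are told immediately.
- *Decision:* expand or close, made on the trial rules. The only expand-or-close rules visible are the DLT counts, and 1/3 gives expansion.
- *Release:* allowed if the IRB and DSMB have imposed nothing further.
- *Result:* three more subjects can be assigned to the same dose.

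**2. Where the DSMB's own tasks fall on this path.** The causality review and the closure determination have no stated deadline, and neither is named as a precondition for restoring access. If both are still open, the condition that no restriction has been imposed is nevertheless satisfied.

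**3. The zone rule does not fill the gap.** A new zone opens only when all subjects in the previous zone have completed the trial. That delays escalation, but rule (3) expands within the same zone.

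**4. How often the release step may be used, for a DLT of any grade.** Input: a DLT rate p of 5% to 8% (IV, ii, Total Planned Enrollment). Subjects and arms are treated as independent.

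P(exactly 1 DLT in 3) = 3p(1−p)²

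- p = 0.05: 3 × 0.05 × 0.95² = 0.135
- p = 0.08: 3 × 0.08 × 0.92² = 0.203

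P(at least one arm expands) = 1 − (1 − P)ⁿ

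- 9 arms (27 subjects ÷ 3, the low end of the plan's simulated range), p = 0.05: 1 − 0.8646⁹ = 0.73
- 12 arms (all combinations listed), p = 0.08: 1 − 0.7969¹² = 0.93

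Closures would reduce the number of arms tested. The documents do not say what share of DLTs would be related grade 4 or 5 events, so none of these figures measures that scenario.

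**The case against.** The strongest reply is that the plan already covers most of this risk. All enrollment stops. The DSMB chair hears of a life-threatening or fatal event at once, and the board's authority includes temporary closure, so a board that wants more time can take it. For harm to follow, the chair would have to know of a related death and do nothing while the PI, who made the report, reopened the trial. This largely stands, and it is why the point is small.

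Second, the text can be read differently. The term for the trial rules is not defined as the DLT counts alone. Since the closure determination belongs to the DSMB with the IRB, the decision that precedes release might be taken to include theirs. This stands in part. But the same sentence mentions the DSMB separately, as a body that has been notified and has not objected. If both readings are possible, one added sentence settles the matter.

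Third, the appendix table of delegated responsibilities, which has a column for the monitoring committee, was available only in part. Its rows assign tasks, so they are unlikely to change the release condition written in the Study Procedure section. This remains a limit on certainty.

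Fourth, the scenario may be rare. The Background describes oral NAC side effects as generally minor. In the cited phase I trial of up to 1800 mg three times daily, 9 of 11 drug-related events were gastrointestinal and all 11 resolved, 3 of them after dose reduction. This stands: the documents give no reason to expect many such events.

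**Conclusion.** The point holds in a narrow form. As written, release after a related grade 4 or 5 event rests on non-objection following a decision that ignores grade, so it can come before the DSMB has finished its review. This rests on the visible text, on reading the trial rules as the DLT counts, and on applying rule (3) to every arm.

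Three stronger readings are not supported:

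- A reader might infer that the plan has no stop after a serious event, or no DSMB role. It has both.
- A reader might take the 73% to 93% chance of at least one expansion as the chance of the unsafe sequence. Those figures, like the 13.5% to 20.3% per arm, count DLTs of every grade, including grade 3 events for which no change is proposed. The frequency of the scenario itself cannot be derived.
- A reader might call this a material design flaw. The suspension, the immediate report and the closure authority already cover most of the risk, and no cohort size, threshold or sample size is affected.

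It is a modest safety tightening that the sponsor should consider.

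**What to change.** Add to the hold-and-release text in Study Procedure, with a cross-reference in rule (3):

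> After any grade 4 or grade 5 event judged at least possibly related to study drug, User Rights are restored and expansion proceeds only after a recorded DSMB decision. That decision completes the causality review and the continue-or-close determination, and states whether subjects still taking that dose should stop or be notified. Absence of an objection is not clearance. Grade 3 DLTs follow the existing path.

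**Cost.** A few sentences in an amendment, using the existing board and the existing access lock. DLT rules, cohort sizes and planned enrollment do not change.

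**Downside.** A short accrual pause, which affects all arms because the lock is trial-wide. COVID-19 deterioration will sometimes trigger it. A possible relationship needs only two of four criteria, and difficulty breathing and pneumonia are listed famotidine reactions, so timing plus a known pattern could be enough. The burden is limited because the severity table grades hospitalization alone as severe, which keeps the current path. The added condition applies to life-threatening or intensive-care-level events and to deaths.
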